## 5.6.b. Data Analysis

**Power and Sample Size Calculations.** This study is powered on weight change at six months, comparing intervention and control conditions. We used formulas specified by Friedman et al. for use in clustered randomized controlled designs. Sample size was calculated for continuous outcomes and inflated to account for clustered randomization, using the inflation factor  $1 + (m - 1)\rho$  for cluster size  $m$  and intraclass correlation  $\rho$ , and attrition. Based on outcomes in prior weight loss trials, **we expect those in *MOVE!+UP* to lose 12 pounds on average, which would likely correspond to clinically meaningful weight loss (5% of baseline weight).** The specified expected weight loss is plausible, given *MOVE!+UP* pilot participants lost an average of 14 pounds, corresponding to 6% of baseline weight. We expect those in the control condition to achieve weight loss of 3.6 pounds on average consistent with Veterans with PTSD who participate in *MOVE!*, according to administrative data.

In the power calculation, the standard deviation of the outcome was assumed to be 13 based on previous findings. We calculated this value based on the marginal SD of 50 for baseline weight observed among Veterans with PTSD in *MOVE!*, between baseline and 6-month weight observed in the *MOVE!+UP* pilot (comparable to other weight loss effectiveness trials). Comparing these outcomes, an 8.4 pound difference in weight lost corresponds to prior behavioral weight loss trials and would yield a medium Cohen's  $d$  effect size of 0.65.

Table 7 displays the sample size required for varying cluster sizes *m* and intraclass correlation coefficients  $\rho$  assuming 90% power. The sample size of N=164 total Veterans (82 Veterans per treatment arm) chosen for this study assumes an ICC of 0.03, cluster size of 8 Veterans per randomized group, 90% power, a two-sided  $\alpha$  of 0.05, and a 6-month attrition rate of 25%, similar to MOVE!+UP pilot’s overall retention and a meta-analysis of missing data in weight loss RCTs. We will also be powered to detect a meaningful change in PTSD symptoms in the intervention condition at six months, aligned with the average PTSD symptom reduction of 18 (SD=12) observed among MOVE!+UP pilot cohort 5 participants and assuming a 9-point clinically meaningful reduction in the control condition.

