**Table 7. Sample size considerations for MOVE!+UP hybrid type 1 trial**

ICC ( $\rho$ )	Cluster size (m)	Total Sample Size
0.05	10	196
0.05	8	182
0.03	10	172
0.03	8	164
0.01	10	148
0.01	8	144
Note: assumes a two-sided $\alpha$ 0.05, 90% power, a 12 – 3.6 = 8.4 lb difference in weight loss between groups, a weight change SD of 13, a 0.97 within-person correlation, and 25% attrition. The bolded row displays the selected parameters for the proposed study.		

**Quantitative Statistical Analysis Overview: Aims 1 and 2.** We will use intent-to-treat analyses to assess differences between intervention and control arms. We will use mixed effects models to account for clustering since participants in the intervention arm in the same enrollment cohort receive group treatment together. We will attempt to reduce attrition and missing data, which can lead to selection bias.

**Missing data.** In descriptive analyses, we will report summary statistics on proportion of patients with missing data in each of the study arms. We will report overall rates of missing data as well as specific rates for important variables such as study outcomes and baseline adjustment variables. We will provide descriptive statistics summarizing associations between available auxiliary variables and missingness in important model variables.

Methods for handling missing data in the primary analyses will be pre-specified and not influenced by the descriptive analyses described above. Missing data in the primary and secondary analyses will be accounted for through multiple imputation (MI) methods described below. Prior to multiple imputation, we will attempt to fill in missing baseline values of African-American race/ethnicity from the EHR.

Analyses of primary and secondary outcomes will account for missing data in outcome or baseline adjustment variables through Multiple Imputation (MI). We will perform MI using the Multiple Imputation by Chained Equations (MICE) method. MICE is a general purpose MI method that can handle missingness in variables of mixed data types (e.g. continuous and categorical) as well as

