clustered data. Missing values will be imputed separately for each faux treatment group. MI will be performed using the outcome and baseline variables pre-specified for adjustment, and pre-specified auxiliary variables that are either likely associated with missingness and/or the outcome (gender, age, race, employment status, educational attainment, medication usage associated with a) substantial weight loss or b) substantial weight gain). We will create 50 imputed datasets, which will then be analyzed and combined according to Rubin’s rules for multiple imputation.

MICE requires specifying a statistical model to generate predictions for each variable with missingness. Table 9 lists the statistical models for each variable that will be used in the imputation procedure. Final imputed values will be based on the predictive mean matching approach, which can provide more plausible values when the distribution of a variable exhibits features such as bimodality or skewness.

Imputation Models

Variable Name	Variable Type	Statistical Model for MICE procedure	Rationale for inclusion
6-month Weight	Continuous	Linear regression	Outcome being imputed
Baseline Weight	Continuous	Linear regression	Typically associated with outcome
African-American race/ethnicity	Binary	Logistic regression	Typically associated with outcome and with missingness in a prior WL trial among Veterans
Employment status	Categorical	Multinomial regression	Associated with missingness in a prior WL trial among Veterans
Educational achievement	Categorical	Multinomial regression	Associated with missingness in a prior WL trial

 Citation: <https://www.ncbi.nlm.nih.gov/pmc/articles/PMC6408317/>

			among Veterans
Age	Continuous	Linear regression	Associated with missingness in a prior WL trial among Veterans
Gender	Categorical	Multinomial regression	Typically associated with outcome and was associated with missingness in a prior WL trial among Veterans
Weight management medication usage in the 6 mos following enrollment (Yes vs. no)	Binary	Logistic regression	Typically associated with outcome
Weight gain meds in the 6 mos following enrollment (Yes vs. no)	Binary	Logistic regression	Typically associated with outcome

**References:** Prior WL trial among Veterans: <https://jamanetwork.com/journals/jama/fullarticle/2799407>; [name] will add references for gender, Af-Am race

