Sensitivity analyses:  Including auxiliary variables to assess impact of missing data	1. 6-month absolute weight change from baseline (pounds) 2.	Binary treatment indicator  Baseline outcome  Binary African-American indicator (weight analyses only)  Auxiliary variables discussed in the Handling of Missing Data section. Plus those that appeared possibly associated with missingness on 6-month weight in descriptive comparisons.
Sensitivity: bariatric surgery	1. 6-month absolute weight change from baseline (pounds) 2. 12-month absolute weight change	Binary treatment indicator

Analysis	Outcome(s)	Independent Variables
influence	from baseline (pounds)	
Baseline outcome
 
Binary African-American indicator (weight analyses only)
 
Remove veteran outcome with bariatric surgery. However no one had bariatric surgery during the study period so this analysis is not being conducted.

Sensitivity analysis: examine differences in utilization across tx conditions and the influence of these factors on weight loss outcome.	
 
1. 6-month absolute weight change from baseline (pounds)
 
2. 12-month absolute weight change from baseline (pounds)
 
3.
 
	
Binary treatment indicator
 
Baseline outcome
 
Binary African-American indicator (weight analyses only)
 
-Binary indicator of prescription weight loss medications from baseline to 6 and 12 months reported in EHR and/or self report
 
-binary indicator of non-MOVE! +UP/MOVE! weight management care (i.e., any self-reported non-Va program, dietician visits TeleMOVE!). Will not include self-reported use of websites, Fitbits etc.
 
If the pattern of results changes from what was found in the primary analysis, we would pursue a formal mediation analysis.

Sensitivity analysis: If we see substantial issues with the q-q plots when the primary analysis is	
 
1. 6-month log-transformed weight change from baseline (pounds)
 
1.
 
	
Binary treatment indicator
 
Baseline outcome
 
Binary African-American indicator (weight analyses only)

Analysis	Outcome(s)	Independent Variables
run, we will do a sensitivity analysis with a log-transformed outcome		

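### The only sensitivity analysis labelled for missing data cannot examine departures from missing at random, and it adjusts the treatment effect for medication use after randomisation

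*Combined protocol and SAP*

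**What the plan says.** The Missing data part of section 5.6.b handles missing primary and secondary outcomes by multiple imputation: "We will perform MI using the Multiple Imputation by Chained Equations (MICE) method". There are 50 imputed datasets, and "Missing values will be imputed separately for each faux treatment group". The imputation model for 6-month weight uses baseline weight, African-American race/ethnicity, employment, education, age, gender and two medication indicators: "Weight management medication usage in the 6 mos following enrollment (Yes vs. no") and "Weight gain meds in the 6 mos following enrollment (Yes vs. no").

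The Statistical Models table in the same section has one sensitivity row on missing data, labelled "Including auxiliary variables to assess impact of missing data". As the text stands, it lists only 6-month weight change. Besides arm, baseline weight and race, its independent variables are "Auxiliary variables discussed in the Handling of Missing Data section", followed by "Plus those that appeared possibly associated with missingness on 6-month weight in descriptive comparisons".

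The other sensitivity rows cover prior weight-loss treatment, prior mental health treatment, bariatric surgery, utilization during follow-up and a log transformation. No delta-adjusted, tipping-point, pattern-mixture or reference-based analysis appears. The sample size assumes "a 6-month attrition rate of 25" per cent.

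**The concern.** A sensitivity analysis for missing data should vary the assumption that the primary analysis cannot verify. Here that assumption is that, given the imputation variables, missing weights follow the same distribution as observed ones. The documents do not name MAR, but the imputation specification implies it. Entering the same auxiliaries as covariates, with more observed predictors of missingness, broadens the set of variables conditioned on. It does not allow missing participants to differ from observed participants with the same recorded characteristics.

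The imputation model contains no weight between baseline and 6 months and no attendance measure, so MAR rests on baseline characteristics and two medication flags. A participant who dropped out because the programme was not working would be imputed as though it had worked about as well as for comparable completers in the same arm.

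The row also has a defect of its own. Under section 5.5, randomisation follows consent and baseline measures, so medication use in the 6 months after enrollment falls essentially after randomisation. If the arms differ in that use, adjusting for it removes part of the treatment effect. Agreement with the primary result would therefore say nothing about departures from MAR, and disagreement could come from the medication adjustment.

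**Working it through.** **Inputs.** From section 5.6.b and Table 7: expected losses of 12 and 3.6 lb (difference 8.4 lb), SD of weight change 13 lb, ICC 0.03, cluster size 8, two-sided alpha 0.05, 90% power, 25% attrition, 82 per arm. From the abstract: 174 randomised (87 per arm if equal).

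**Reproducing the plan's figure.**
- n per arm = 2 × [13 × (1.960 + 1.282) / 8.4]² = 50.33.
- Design effect = 1 + (8 − 1) × 0.03 = 1.21.
- 50.33 × 1.21 / 0.75 = 81.2, rounded up to 82 per arm, 164 in total. This matches, and the same formula reproduces all six rows of Table 7.

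The 25% is thus a genuine planning input. Inflating N for it protects precision, not against bias.

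**Effect of a departure from MAR.** Let p be the proportion missing in an arm, and d the number of pounds by which its missing participants do worse than imputed.
- Adjusted effect = MAR estimate − (p_I × d_I − p_C × d_C), where I is MOVE!+UP and C is control.
- With p = 0.25 in both arms, the shift is 0.25 × (d_I − d_C). Equal deltas cancel.
- With d_C = 0 and an estimate of 8.4 lb: d_I = 4 gives 7.4 lb; d_I = 8.4 (missing participants resemble controls) gives 6.3 lb; d_I = 12 (back to baseline weight) gives 5.4 lb.

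**Where significance is lost.** SE = 13 × √(2 × 1.21 / completers per arm), held fixed as d varies.
- 164 randomised: 61.5 completers per arm, SE 2.58 lb, smallest significant difference 1.96 × 2.58 = 5.05 lb.
- 174 randomised: 65.25 completers per arm, SE 2.50 lb, smallest significant difference 4.91 lb.
- Tipping d = (estimate − smallest significant difference) / 0.25.

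| MAR estimate (lb) | Tipping d, N = 164 | Tipping d, N = 174 |
|---|---|---|
| 8.4 | 13.4 | 14.0 |
| 7.0 | 7.8 | 8.4 |
| 6.0 | 3.8 | 4.4 |
| 5.5 | 1.8 | 2.4 |

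The estimates below 8.4 lb are illustrative.

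**Would the planned row detect a problem?** Two large simulated samples were analysed by regression on the observed cases, without clustering or imputation. The settings are assumptions, not figures from the documents.
- *Departure from MAR:* missing MOVE!+UP participants lose 12 lb less, and medication use is equal across arms. The true effect is 5.5 lb. The estimate is 8.5 lb with baseline weight alone and 8.5 lb after adding auxiliaries (age and the two medication indicators). The row would show no change despite a bias of 3 lb.
- *No departure from MAR:* weight-loss medication use is 20% in MOVE!+UP and 10% in control, with an 8 lb medication effect. Adding the auxiliaries moves the estimate from 9.2 to 8.4 lb. The shift is 8 × 0.10 = 0.8 lb, which is adjustment for a mediator.

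**The case against.** Several points on the other side are fair.

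- **The row does more than repeat the imputation variables.** It also adds variables that look related to missingness, so it can reveal sensitivity to observed predictors left out of the imputation model. That stands, but it remains an analysis conditional on observed data.
- **Data-driven selection is contained.** The Missing data text says the primary methods are pre-specified and will not be influenced by the descriptive comparisons. The selection affects one supportive row.
- **The plan limits and describes missingness.** Imputation is by group, so relationships may differ by arm; missingness is reported by arm; assessments are paid; and a lost-to-follow-up protocol applies. Weight is taken at home on a study scale at virtual visits, so a participant who skips sessions need not have a missing outcome. These measures reduce the risk without showing how much it would matter.
- **The mediator role is recognised elsewhere.** The utilization row adjusts for weight-loss medication during follow-up and foresees a mediation analysis if results change. That supports keeping such variables out of a row meant for missing data.
- **The planned effect is sturdy.** At 8.4 lb, even a full return to baseline among missing MOVE!+UP participants leaves 5.4 lb, above the 5.05 lb threshold. This is correct; fragility arises only with a more modest estimate.

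A reader might go further and say that the plan fails to test MAR. MAR cannot be tested from observed data, and the plan does not claim to test it. The gap is that departures from it are never explored.

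**Conclusion.** The concern holds for the sensitivity analysis. The plan has no analysis that examines departures from the MAR assumption implied by its imputation, and its one row on missing data adjusts for two post-randomisation variables.

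The consequence depends on the result. A conclusion based on an estimate near 8.4 lb would survive a shift of about 13 to 14 lb in the missing MOVE!+UP participants. One based on 5.5 lb would be lost at about 2 lb. These figures assume 25% missing in each arm, controls missing at random, the plan's SD and design effect applied to both arms, a normal approximation and a fixed SE. The documents do not give actual missingness.

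Two further inferences are not supported. The documents do not show that the primary estimate is biased; whether missing participants did worse is unknown. Nor does the primary model adjust for follow-up medication: its covariates are baseline weight and race, and the medication indicators enter only through imputation.

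**What to change.** Keep the primary analysis as it is, and add to the SAP:

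- A delta-adjusted multiple imputation of 6-month weight. Add pre-specified deltas to the imputed weights, first in MOVE!+UP only and then with unequal deltas in the two arms. Extend the grid until the conclusion tips, and report the tipping point with the estimate and interval at each step. An equal delta in both arms is not useful alone, because it largely cancels when missingness is similar.
- Optionally, one reference-based run in which missing MOVE!+UP outcomes are imputed from the control-arm model. This departs from the planned within-group imputation and needs its own specification.

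If the covariate row is kept, restrict it to pre-specified baseline auxiliaries, and use the post-enrollment medication variables in the imputation model only.

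The cost is SAP wording and a few extra runs, with no new data. The deltas have no source in the documents and must be justified as assumptions. The abstract reports no findings to date; on that footing the change can be fixed before results are known.

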### **Interventions.**

- Control group participants participated in the VA's standard *MOVE!* Program, delivered as part of usual care. *MOVE!* is an evidence-based program for obesity management. The curriculum uses cognitive-behavioral techniques like goal setting and self-monitoring and applying autonomy-supporting counseling like motivational interviewing mostly in in-person group sessions. *MOVE!* control participants participated via VA Video Connect (VVC). Participants were able to express an interest in other *MOVE!* modalities as well, if preferred, though the study encouraged participation in the group-based modality, to ensure comparability across treatment arms.

Those randomized to the intervention group received *MOVE!+UP*, a program co-led by a psychologist with specialized PTSD training and a Veteran peer support counselor. It consists of 16 group sessions that involve general *MOVE!* weight loss support (e.g., goal setting, nutrition guidance, activity/diet monitoring). However, to address PTSD-related barriers, *MOVE!+UP* also incorporates CBT elements such as addressing unhelpful thinking patterns, relationship support, and sleep hygiene. Each

session also includes a 30-minute community walk because activity increases retention in *MOVE!*, and to address hypervigilance-based activity barriers through experiential learning. *MOVE!+UP* also provides two individual dietician visits. As-needed counseling calls and coordination with medical, mental health, and/or social services are also provided. *MOVE!+UP* sessions were offered by VVC and over the telephone using a backup conference line for those who may prefer to dial in and do not want to or cannot access VVC, dietician visits were held by phone or VVC, and the community walk was done individually during *MOVE!+UP* sessions in Veterans' own communities.

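### The utilization sensitivity row adjusts the weight effect for medication and care used during follow-up, so its treatment coefficient is in general neither the ITT effect nor an identified direct effect, and it should not trigger mediation analysis

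*Combined protocol and SAP*

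**What the plan says.** Section 5.6.b makes Aims 1 and 2 intention-to-treat. The primary model for 6-month weight change contains the treatment indicator, baseline weight, an African-American indicator and a random intercept for treatment group.

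The statistical models table in the same section then lists a sensitivity row on utilization, for weight change at 6 and 12 months. Its stated aim is to look at how utilization differs between conditions and how it influences weight loss. It keeps the primary covariates and adds two items:

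- "Binary indicator of prescription weight loss medications from baseline to 6 and 12 months reported in EHR and/or self report";
- a binary indicator of weight management care outside MOVE!+UP and MOVE!, which counts self-reported non-VA programmes, dietician visits and TeleMOVE!, with no time window given.

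The row ends with a rule: "If the pattern of results changes from what was found in the primary analysis, we would pursue a formal mediation analysis". It does not define a changed pattern, name an estimand, list common causes of utilization and weight, or say how the mediation analysis would be done.

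An earlier row in the same table adjusts instead for weight-loss medication at baseline and MOVE! visits in the preceding year. On access to care, Section 5.1 says of the control arm: "Participants were able to express an interest in other" MOVE! modalities. Section 5.5 says those randomised to MOVE!+UP were told not to use MOVE!. MOVE!+UP itself includes two dietician visits.

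**The concern.** Medication and outside care during follow-up come after assignment. A participant who is losing little weight may seek a prescription, and a participant in the richer programme may not need one. Motivation, appetite, comorbidity and access to care can drive both utilization and weight, and two baseline covariates do not capture them. Putting such a variable in the outcome model removes any part of the treatment effect that runs through it. It also opens a non-causal path between arm and weight through the shared causes.

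The row sits in a list of sensitivity analyses, so readers may take agreement with the primary estimate as reassurance and disagreement as doubt. Neither inference is safe. The trigger builds the same inference into the plan.

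**Working it through.** **The plan's own figures.** Table 7 gives the anchors: "8.4 lb difference in weight loss between groups, a weight change SD of 13", with "a 0.97 within-person correlation, and 25% attrition", and Section 5.6.b a "cluster size of 8 Veterans per randomized group" with ICC 0.03.

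- n per arm = 2 x (SD x (z0.975 + z0.90) / delta)^2 = 2 x (13 x 3.2415 / 8.4)^2 = 50.33
- Design effect = 1 + (8 - 1) x 0.03 = 1.21
- 50.33 x 1.21 / (1 - 0.25) = 81.2, rounded up to 82 per arm, 164 in total

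This matches the stated "82 Veterans per treatment arm". The other five rows of Table 7 also reproduce. Nothing below changes these figures; they only set the scale.

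**Why the coefficient moves.** Let p0 and p1 be the proportions using a co-treatment M in the control and intervention arms, g its true effect on weight, and b its fitted coefficient. Leaving out the baseline covariates, least squares gives:

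- adjusted coefficient = ITT - b x (p1 - p0)
- direct effect = ITT - g x (p1 - p0)
- so adjusted - direct = -(b - g) x (p1 - p0)

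If p1 = p0, the adjusted coefficient is the ITT effect. If use and weight share no unmeasured cause, b = g and it is the direct effect. Otherwise it is neither.

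**Illustration 1.** Simulation of 2 million subjects, least squares, no cluster term, with ITT fixed at the plan's -8.4 lb and SD about 13. Utilization, g and the unmeasured cause U are all assumed. U is described by its effect on weight per SD and its latent correlation with M.

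| Use, control / MOVE!+UP | g (lb) | U: lb per SD, correlation | Direct effect | b | Adjusted coefficient |
|---|---|---|---|---|---|
| 15% / 15% | -10 | 5, 0.5 | -8.4 | -5.38 | -8.40 |
| 30% / 10% | -10 | none | -10.4 | -10.00 | -10.42 |
| 30% / 10% | -10 | 5, 0.5 | -10.4 | -5.63 | -9.53 |
| 30% / 10% | -10 | -5, 0.5 | -10.4 | -14.38 | -11.27 |
| 30% / 10% | -10 | 8, 0.7 | -10.4 | -0.17 | -8.45 |
| 30% / 10% | 0 | 5, 0.5 | -8.4 | 4.39 | -7.51 |
| 30% / 10% | 0 | -5, 0.5 | -8.4 | -4.38 | -9.26 |

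Check on the third line: -(-5.63 + 10) x (0.10 - 0.30) = 0.87, and -10.4 + 0.87 = -9.53.

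**What this means for the trigger.**

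- With an effective co-treatment used unequally and no confounding, the coefficient moves from -8.4 to -10.4 lb. Nothing is wrong with the primary result.
- With no co-treatment effect at all, it still moves to about -7.5 or -9.3 lb. Confounding has created a change.
- In the fifth line it stays at -8.45 lb although the direct effect is -10.4 lb. Confounding has hidden a change.

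**Illustration 2: size, and an obvious alternative.** Assumed: direct effect -8.4 lb, g = -15 lb, U worth 5 lb per SD on weight (either sign) and a log-odds of 1 per SD on medication start. The total effect is -8.4 + (-15) x (0.10 - 0.20) = -6.9 lb at 20% vs 10% use, and -8.4 + (-15) x (0.10 - 0.30) = -5.4 lb at 30% vs 10%. The last column sets weight to missing after medication start and imputes within arm under missing at random (MAR).

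| Use, control / MOVE!+UP | Total effect | Adjusted coefficient | Set to missing, MAR |
|---|---|---|---|
| 20% / 10% | -6.9 | -7.96 or -8.82 | -7.99 or -8.79 |
| 30% / 10% | -5.4 | -7.49 or -9.29 | -7.53 or -9.25 |

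Bias against the direct effect is about 0.4 lb in the first line (8.4 - 7.96 = 0.44; 8.82 - 8.4 = 0.42) and about 0.9 lb in the second (0.91; 0.89). At 6% vs 3% use it is about 0.15 lb. The imputation alternative has nearly the same bias, because U breaks MAR just as it confounds the covariate adjustment.

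**The case against.** The best defence is that the row does not claim to be an ITT estimate. Its stated aim is the influence of utilization on weight, and naming mediation analysis as the next step shows that the authors see these variables as possible mediators. The primary analysis is ITT with baseline covariates only, and nothing lets this row overturn it. All of that stands. It limits the consequence but leaves the coefficient and the trigger without a defined meaning.

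The defence is also right on four stronger readings that a reader might infer:

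- **That the coefficient is always wrong.** It is not. It equals the ITT effect when use is balanced, and no document reports imbalance.
- **That every co-treatment begins after randomisation.** The medication indicator counts use from baseline onward, so it can include prescriptions already running.
- **That the medication window overruns the 6-month outcome.** The row lists 6- and 12-month outcomes, and the natural reading pairs each window with its own outcome. The text only needs to say so.
- **That counting TeleMOVE! as outside care adjusts away part of the control condition.** Section 5.1 says control participants could express interest in other modalities. It does not name TeleMOVE! and says the study encouraged the group format. Section 5.1 also separates TeleMOVE! from standard MOVE! for eligibility. Uptake is not reported. What remains is that the row has no rule separating programme visits from outside ones.

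**Conclusion.** The concern holds for the utilization row and its trigger, and no further. The treatment coefficient from that row is in general neither the ITT effect nor an identified direct effect, because the plan does not argue either condition that would make it one. A change in the result is expected whenever an effective co-treatment is used unequally, and confounding can create or hide a change. The trigger is therefore unreliable in both directions.

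The size cannot be read from the documents. Under the assumed confounding, bias against the direct effect runs from about 0.15 lb at 6% vs 3% use to about 0.9 lb at 30% vs 10%, on a planned difference of 8.4 lb. Stronger confounding gives more. The primary ITT test, its alpha and the sample size of 164 are untouched, and the documents do not support reading this as a flaw in the primary result.

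**What to change.** In the SAP:

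1. Report medication and other weight care used after randomisation by arm, descriptively.
2. Remove the covariate-adjusted coefficient, or state that it is not a check on the primary result. For adjustment, rely on the existing row that uses baseline medication and prior MOVE! visits.
3. Delete the rule that a changed pattern leads to mediation analysis.
4. If a direct effect is wanted, pre-specify the mediation estimand, the mediator-outcome confounders and a sensitivity analysis for unmeasured confounding.
5. State that the 6-month window goes with the 6-month outcome and the 12-month window with the 12-month outcome. State also that MOVE! modalities and dietician visits received as part of the assigned programme are not outside care.

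Setting weight to missing after medication start and imputing under MAR should not be offered as a bias-free replacement. It carries the same unmeasured-confounding bias. The imputation model in Section 5.6.b would also need changing, because it already contains weight management medication used in the 6 months after enrolment.

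The cost is a little more SAP wording and the loss or demotion of one sensitivity row. Item 4 adds work only if a direct effect is wanted.
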